Anhedonic adolescents will undergo a 12-week protocol of BA treatment. Neural (fMRI) and behavioral (PRT) measures will be assessed at pre- and post-treatment, and the EMA protocol will involve repeated assessment waves. We hypothesize that:

PARTNERS HUMAN RESEARCH COMMITTEE DETAILED PROTOCOL

- (a) Pre-treatment reward dysfunction (i.e., assessed via baseline fMRI, PRT and EMA), controlling for overall pre-treatment levels of depressive symptoms, will predict anhedonic (Snaith–Hamilton Pleasure Scale [SHAPS; Snaith et al., 1995]) symptom improvement over the course of BA.
- (b) Greater pre- to post-treatment normalization in neural (i.e., striatal and mPFC response to fMRI task) and behavioral (i.e., PRT performance) measures will be linked to greater anhedonic symptom improvement over the course of treatment.
- (c) Given emerging evidence of decreased cortico-striatal functional connectivity to reward-related stimuli in depression (Admon et al., 2015), we expect that BA will result in significant increases in cortico-striatal functional connectivity to rewarding stimuli from pre- to post-treatment.

(3) **Specific Aim 3:** Examine association between changes in neural reward circuitry and real-world positive affect and anhedonia: The EMA protocol will be implemented to acquire a more fine-grained and “real-world” assessment of changes in subjective positive affect (PA) and anhedonia, as well as the acquisition and use of BA skills, over the course of treatment. We hypothesize that:

- (a) Following BA, participants will report improvements in daily PA and anhedonia and increased use of BA skills.
- (b) Integrating across units of analyses (i.e., neural, behavioral and self-report), we expect that greater pre- to post-treatment normalization of striatal and mPFC response, cortico-striatal connectivity, as well as PRT performance will be associated with greater improvements in daily reports of PA and reduced anhedonia, as well as use of BA skills.

III. SUBJECT SELECTION

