This study will include two adolescent cohorts, and a parent for each adolescent participant. Rather than recruiting adolescents on the basis of DSM-defined Major Depressive Disorder (MDD), and in line with the NIMH RDoC initiative, the proposed study will recruit treatment-seeking adolescents with elevated anhedonia (as defined by the SHAPS) into a brief clinical trial of BA, as well as a healthy control group for comparison. Specifically, the two adolescent cohorts will consist of: (A) **Anhedonic Adolescents:** Adolescents who report SHAPS scores ≥ 3 ; (B) **Healthy Controls:** Adolescents with no lifetime history of psychopathology and with SHAPS scores = 0. Finally, we also propose to include (C) one parent of each participating adolescent to complete questionnaires assessing their child's, as well as their own, mental health. All participants will complete an initial assessment at McLean Hospital. Within the subsequent week, participants meeting study criteria will be invited back to the lab to collect fMRI data probing reward circuitry function. They will also complete a behavioral task (PRT) assessing reward responsiveness outside the scanner. Anhedonic adolescents completing BA treatment will also fill out self-report measures at the start of each therapy session (see **Table 1**). Following treatment, participants will complete a post-treatment assessment within 10 days of the last session, which will be identical to the pre-treatment session. Although not receiving BA, the healthy control participants will complete corresponding pre-treatment (i.e., initial) and post-treatment (i.e., final) assessments,

PARTNERS HUMAN RESEARCH COMMITTEE DETAILED PROTOCOL

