which will allow for modeling the effects of repeated scans and practice effects (e.g., on the PRT). In addition, a smartphone-based EMA protocol will be implemented for both the anhedonic sample and healthy control sample involving repeated assessments of positive affect (PA) and anhedonia. The EMA protocol will use a smartphone app (*Beiwe*) already approved by both the Partners IRB (protocols 2015P001303; 2012P000890; 2015P000666) and Partners Research Information Security Office (RISO; see attached *RISO Approval for Beiwe EMA Application*). The latter app will be used for Android phones. For participants with iPhones, EMA data will be collected using the *Metricwire* app previously approved by RISO (see attached *RISO Approval for Metricwire EMA Application*) and the IRB (protocol 2015P001303). The schema outlining the assessment procedure is presented in **Table 1**.

Adolescent Cohort

General Inclusion Criteria:

- Both genders, any ethnicity
- Ages 13-18
- English as first language or English fluency
- Smartphone with iOS or Android platform (for EMA)
- *Healthy Control Sample:* Total SHAPS score = 0; *Anhedonic Sample:* Total SHAPS score ≥ 3 . The anhedonic sample must also meet criteria for elevated anhedonia on the K-SADS clinical interview (i.e., anhedonia item score > 1).

General Exclusion Criteria:

- History of head trauma with loss of consciousness for two minutes or more
- History of seizure disorder
- Serious or unstable medical illness, including cardiovascular, hepatic, renal, respiratory, endocrine, neurologic or hematologic disease
- Current use of cocaine or stimulant (e.g., amphetamine, cocaine, methamphetamine)
- Current use of dopaminergic drugs (including methylphenidate)
- Clinical or laboratory evidence of hypothyroidism
- Systemic medical or neurological illness that could impact fMRI measures of cerebral blood flow
- Color blindness
- Meet standard exclusion criteria for fMRI scanning (e.g. claustrophobia, cardiac pacemakers, neural pacemakers, surgically implanted metal devices, cochlear implants, metal braces, or other metal objects in their body);
- Positive urine pregnancy test
- Meets criteria for anorexia nervosa (DSM-5 diagnostic code: 307.1) or bulimia nervosa (DSM-5 diagnostic code: 307.51)

**PARTNERS HUMAN RESEARCH COMMITTEE
DETAILED PROTOCOL**

A. Anhedonic Adolescents: Anticipated enrollment = 65

Additional Exclusion Criteria:

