The adolescent portion of the study includes the following cohorts: (a) 35 anhedonic adolescents receiving BA and (b) 35 healthy control adolescents. The primary aim is to examine whether anhedonic and healthy adolescents differ on baseline neural (fMRI), behavioral (PRT) and self-report (EMA) measures of reward function, as well as whether behavioral and neural mechanisms prospectively predict and mediate symptom improvement among anhedonic adolescents receiving BA. Importantly, within the active treatment cohort, analyses will be conducted to determine if there are statistical differences in symptom, behavioral, and/or neural measurements between medicated and non-medicated depressed adolescents. Additional analyses will examine if there are statistical differences between participants on SSRIs versus participants on SSRIs plus other psychiatric medications.

Descriptive and Exploratory Analyses:

Descriptive statistics and exploratory graphical techniques, such as frequencies, means, medians, histograms, and box plots will be used to assess skewness and/or outliers in the data. Continuous/quantitative variables will be appropriately transformed when necessary, e.g., via log transformation for positively skewed distributions. For outcomes acquired during treatment, the analytical approach will address the type of outcome, as well as accommodating the within-individual correlation due to repeated assessments. In

PARTNERS HUMAN RESEARCH COMMITTEE DETAILED PROTOCOL

addition, the results will be assessed for sensitivity to dropouts or missing data. The primary analysis will be an intent-to-treat analysis, which includes all subjects. Of note, attempts will be made to continue assessing subjects even if they drop out of treatment.

Behavioral Variables:

For the PRT, the primary variable of interest will be *Reward Learning*, operationalized as the increase in response bias (RB) scores from Block 1 to Block 3 [$\Delta RB = RB(\text{Block 3}) - RB(\text{Block 1})$]. This variable was selected because it has been repeatedly linked to current and future anhedonic symptoms (Pizzagalli et al. 2005; 2008).

EMA-Derived Variables:

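### Aim 2(c) credits BA with the rise in connectivity, but untreated healthy controls can remove only repeat-scan and practice effects

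*Combined protocol and SAP*

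**What the plan says.** Section II (Specific Aims), Aim 2(c): "we expect that BA will result in significant increases in cortico-striatal functional connectivity to rewarding stimuli from pre- to post-treatment". The same section sets the treatment: "Anhedonic adolescents will undergo a 12-week protocol of BA treatment". No randomisation, waiting list or untreated anhedonic group is described.

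Section III (Subject Selection) defines the cohorts. The treated cohort is "Adolescents who report SHAPS scores ≥ 3", who must also have an elevated K-SADS anhedonia item. The comparison cohort is "Adolescents with no lifetime history of psychopathology and with SHAPS scores = 0". On retest: "Although not receiving BA, the healthy control participants will complete corresponding pre-treatment (i.e., initial) and post-treatment (i.e., final) assessments", "which will allow for modeling the effects of repeated scans and practice effects". No other purpose is given there for the controls' second assessment.

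Section VI (Statistics) tests Group by Time by Condition for ROI activation and Group by Time for the PRT, with healthy controls as the comparator. SHAPS improvement is modelled by growth curves on session-to-session scores. No connectivity analysis is named for Aim 2(c).

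SSRI doses may change during treatment (Section III, Concomitant Medications; Section VII(f)). A participant who starts an otherwise excluded medication may complete the study (Section VII(i)). Table 1 has one scan before treatment (Pre II) and one after, with SHAPS at Pre I, Pre II, every session and post-treatment.

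**The concern.** To say that BA produces a change, one needs some estimate of what the same kind of adolescent would do over the same weeks without BA. Healthy adolescents at the floor of SHAPS do not supply it. They have no episode to recover from, no therapist contact and, at entry, no psychiatric medication.

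If connectivity rises in the anhedonic cohort and not in the controls, Aim 2(c) as worded would be reported as confirmed. The same pattern could arise with no specific effect of BA. The documents nowhere mention natural recovery, regression to the mean or a limit on causal conclusions, so nothing in the plan holds that reading back.

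**Working it through.** **Step 1. What subtracting the control change removes.** The cohort descriptions in Sections III, V.E and VII give:

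| Source of pre-post change | Anhedonic cohort | Healthy controls | Removed by subtraction? |
|---|---|---|---|
| Repeat scan, practice | Present | Present | Yes, if equal in both |
| Natural recovery | Possible: treatment-seeking, current episodes over 2 years excluded | Nothing to recover from | No |
| Non-specific contact (12 sessions of 50 minutes) | Present | Absent | No |
| SSRI dose change or new medication | Permitted | No psychiatric medication at entry | No |
| Regression to the mean on SHAPS | Downward from a high score | Upward, if at all, from 0 | No |
| BA itself | Present | Absent | No |

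The contrast with controls therefore estimates BA plus the four rows above it, not BA alone.

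**Step 2. Which rivals reach connectivity.** Selection was on SHAPS, and connectivity is measured at a separate visit. Pure measurement error in SHAPS does not carry over to the scan. Regression to the mean reaches connectivity only through a state fluctuation shared by both measures. For Aim 2(c) the more direct rivals are natural recovery, therapy contact and medication change.

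**Step 3. Could these matter at this sample size?** The plan's 35 + 35 (Section VI, Sample Size) comes without alpha, power, effect size or SD, so there is no calculation to reproduce. The following is an illustration with the true BA effect set to zero.

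- From the documents: n = 35 per group.
- Assumed: two-sided alpha 0.05; baseline gap g = 0.5 to 0.8 SD; fraction f = 0.2 to 0.6 of the gap closing for reasons other than BA; scan retest correlation r = 0.4 to 0.7; no change in controls.
- Drift d = g × f. SD of change s = √(2(1 − r)).
- Standard error: s/√n for pre-post change, s√(2/n) for Group by Time.
- Probability of significance = Φ(d/SE − 1.96) + Φ(−d/SE − 1.96).

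Low end (g 0.5, f 0.2, r 0.4): d = 0.10 and s = √1.2 = 1.095. Pre-post SE = 1.095/√35 = 0.185, ratio 0.54, probability 0.084. Group by Time SE = 1.095 × √(2/35) = 0.262, ratio 0.38, probability 0.067.

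High end (g 0.8, f 0.6, r 0.7): d = 0.48 and s = √0.6 = 0.775. Pre-post SE = 0.131, ratio 3.67, probability 0.956. Group by Time SE = 0.185, ratio 2.59, probability 0.736.

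| g | f | r | d | Pre-post | Group by Time |
|---|---|---|---|---|---|
| 0.5 | 0.2 | 0.4 | 0.10 | 0.084 | 0.067 |
| 0.5 | 0.4 | 0.7 | 0.20 | 0.333 | 0.191 |
| 0.8 | 0.4 | 0.4 | 0.32 | 0.408 | 0.231 |
| 0.8 | 0.6 | 0.7 | 0.48 | 0.956 | 0.736 |

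In these cases the test rightly detects a change. The mistake would be to credit it to BA. Section III anticipates enrolment of 65 per adolescent cohort and does not reconcile this with 35. A larger n raises every probability above for the same drift.

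**The case against.** This is a mechanism study with one treated arm, and that is a legitimate choice. The primary aim in Section VI is baseline group differences plus prediction and mediation of improvement, not efficacy of BA. Aims 2(a), 2(b) and 3(b) are predictive or associational, and Aim 2(c) is phrased as an expectation. The controls do serve the purpose that the protocol gives them. The figures above rest wholly on assumptions and span too wide a range to estimate anything. All of this stands, and it limits the point to the wording of Aim 2(c).

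A reader might go further in three ways that the documents do not support.

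- **A large artefact on SHAPS.** Because the cohorts come from opposite ends of SHAPS, one can simulate a Group by Time contrast with no treatment effect and get 0.53 to 1.33 SD (assumed cuts at +1 and −0.5 SD, retest correlation 0.5 to 0.8). But the plan states no Group by Time test of SHAPS. The documents give neither percentiles nor reliability. Controls are also screened on lifetime and family history, so they would regress toward their own low mean, not a pooled one. For ROI activation, the planned interaction with Condition would cancel any regression common to gains and losses.
- **Aim 3(a) has the same fault.** Its wording is temporal (improvement after BA), and its outcomes are EMA reports and skill use, which were not selection variables.
- **The SHAPS run-in can rescue attribution.** Pre I and Pre II are about a week apart, so a slope from three pre-treatment scores is weakly estimated and cannot rule out recovery over 12 weeks. It does nothing for connectivity, which has a single pre-treatment scan.

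**Conclusion.** The point holds for Aim 2(c) and is minor. The attribution to BA is not supported by a design in which all anhedonic participants are treated and the only comparator is healthy and untreated. This conclusion needs no numerical assumption, because it follows from the cohort definitions. How much of an observed change would be due to other causes cannot be derived from the documents. The probabilities of 0.08–0.96 (pre-post) and 0.07–0.74 (Group by Time) show only that, under the stated assumptions, a significant result with no BA effect may be rare or common. The design itself need not change, and the other aims are not affected by this point.

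**What to change.** Restate Aim 2(c), and the conclusion drawn from it, as pre- to post-treatment change in cortico-striatal connectivity over the BA period relative to retest change in healthy controls, not as an effect of BA. Add a sentence that the design does not separate BA from natural recovery, non-specific contact or medication change. Since Section VI names no connectivity analysis, state the comparison with controls there. This needs no new data, visits or participants. The only cost is a weaker claim.

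Optional: SHAPS at Pre I is a selection score, and the plan does not say whether it enters the growth model. A sensitivity analysis could leave it out, or fit a separate pre-treatment phase (Pre I, Pre II, session 1). It should be reported as addressing early regression to the mean on SHAPS only, not natural recovery and not Aim 2(c).

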Paralleling a previously approved protocol ([2012P001844](#)), anhedonic adolescents will receive 12, 50-minute BA sessions. The study will be embedded within a 12-week protocol of BA, implemented following two treatment manuals (Martell et al., 2013; McCauley et al., 2015) co-authored by [name], Ph.D. (consultant). The manuals provide detailed instructions regarding how to administer specific BA procedures and techniques, while providing sufficient flexibility for therapists to adapt treatment to the idiosyncratic needs of patients. As some 18-year-old participants may no longer live at home, 18-year-old (adult) participants who do not live with their parents can do therapy on their own without parent involvement.

During the course of treatment, adolescents will complete self-report measures prior to selected therapy sessions (see **Table 1** for schedule of MFQ, CES-D, SHAPS MASC, WAI-S-C, PSS assessments). Additionally, prior to selected sessions, the study clinicians will complete measures of depression severity (CDRS-R) and the therapeutic alliance (WAI-S-T). Similar to the abovementioned approved protocol (2012P001844), all sessions will be videotaped to assess therapist adherence to the BA treatment manual as well as competence. All participants will consent to videotaping before beginning the study and will be free to leave the study at any time if they are uncomfortable being filmed (see attached consent forms). If a participant does not attend a scheduled session, the study clinician will contact the participant's parent (if the participant is a minor) or the participant directly (if they are 18). If the study clinician leaves a message and the parent or participant does not respond within 24 hours, a second attempt will be made. All attempts to contact parents and subjects about missed sessions will be documented. If the schedule permits, the therapist will attempt to reschedule the session.

BA sessions will be conducted by [name] (Ph.D. in clinical psychology), or clinical psychology Ph.D. students from McLean Hospital's psychology internship program. The internship program is co-directed by [name], Ph.D., ABPP (consultant), who will provide weekly supervision on treatment implementation and supervision of study therapists, supplemented with monthly phone meetings with [name]. Importantly, the internship is based in the Behavioral Health Partial Program

PARTNERS HUMAN RESEARCH COMMITTEE DETAILED PROTOCOL

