
Participants will be contacted at regular intervals to ensure high EMA completion.

PARTNERS HUMAN RESEARCH COMMITTEE DETAILED PROTOCOL

F. Post-Treatment Adolescent Assessment (Approximately 3 hours):

Within 10 days of the final BA session, anhedonic participants will return for a post-treatment assessment lasting approximately 3 hours. Healthy control participants will also complete the same assessment 12-13 weeks after their initial assessment. Adolescents will be asked to complete self-report measures assessing symptoms/affect (MFQ, CES-D, SHAPS, TEPS, MASC, PANAS), stress (PSS, ALEQ-R), cognitive vulnerability (CTI-C, CRSQ, ACSQ), interpersonal vulnerability (CDEQ), personality (NEO-FFI-3), and EMA PANAS Forecasting. Adolescents will also complete the same fMRI task and the PRT task as completed at the pretreatment/baseline assessment.

Parents will complete the same self-report (BDI-II, SHAPS, TEPS, PANAS, PSS) and parent-report measures (MFQ-PR, MASC-PR) as they completed at the initial assessment.

Debriefing for Active Treatment Cohort and Their Parents:

Within one week of concluding post-treatment study session, the treatment group subject and parents will be debriefed. Specifically, the subject and parents will receive a summary including: (a) pre- and post-treatment diagnosis, (b) pre- and post-treatment changes in depressive and anxious symptoms, (c) recommendations for treatment moving forward (if necessary), and (d) a list of clinical resources in the greater Boston community if family is interested and/or would benefit from continuing treatment.

Debriefing for All Subjects

Following the final assessment, all subjects will be debriefed regarding the two monetary reward tasks (i.e., fMRI reward task and the PRT). Specifically, (s)he will outline the purpose of the study and explain the purposes of the scans and tasks. The study staff member will explain the differential reinforcement schedule utilized in the PRT. They will explain the partial contingency between the accuracy of the subject's choices and his/her likelihood of receiving positive feedback, and the rationale for use of this paradigm. Similarly, study staff will explain the our interest in probing reward-circuitry function during reward anticipation and outcome (i.e., wins, losses, neutral outcomes) for the fMRI task.

G. Follow-up Assessments

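### The two cohorts' retests are timed from different anchors, so the control retest interval may not match the anhedonic interval it is meant to correct

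*Combined protocol and SAP*

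**What the plan says.** Section V.F gives two timing rules. For the treated cohort: "Within 10 days of the final BA session, anhedonic participants will return for a post-treatment assessment". Section III says the same: "participants will complete a post-treatment assessment within 10 days of the last session". For controls: "Healthy control participants will also complete the same assessment 12-13 weeks after their initial assessment".

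Section III also explains why controls are retested. Their visits parallel those of the treated cohort, "which will allow for modeling the effects of repeated scans and practice effects".

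Other timing statements that bear on the interval:

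- First scan and PRT, both cohorts (Section III): "Within the subsequent week, participants meeting study criteria will be invited back to the lab to collect fMRI data".
- Length of treatment (Section II, Aim 2): "Anhedonic adolescents will undergo a 12-week protocol of BA treatment".
- Number of sessions (Section V.E): "anhedonic adolescents will receive 12, 50-minute BA sessions".
- Missed sessions (Section V.E): "If the schedule permits, the therapist will attempt to reschedule the session".

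No maximum is stated for the wait between the first scan and session 1, or for the time from session 1 to session 12. Section VI (Statistics) tests Group x Time for the PRT and Group x Time x Condition for each fMRI region of interest. Neither model names the retest interval, and no rule links control timing to the anhedonic cohort.

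**The concern.** A control group can remove retest effects from a Group x Time contrast only if both groups are retested after similar intervals, or if those effects do not depend on the interval. Here the control clock starts at the initial assessment and runs for a set period. The anhedonic clock stops only after the last session, whenever that falls. Late starts and rescheduled sessions lengthen one interval and leave the other unchanged.

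Any part of practice, habituation or repeat-scan change that depends on elapsed time would then differ by group and could be read as normalization after BA. For fMRI there is a second consequence. Only regions with a significant interaction supply change scores to the growth models for the Snaith-Hamilton Pleasure Scale (SHAPS), so a timing artefact could influence which regions go forward.

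**Working it through.** **Inputs from the protocol**

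- Control retest: 12-13 weeks after the initial assessment, i.e. 12 x 7 = 84 to 13 x 7 = 91 days (Section V.F).
- Initial assessment (Day 1) to first scan and PRT (Day 2): 0-7 days (Section III).
- Sessions: 12 (Section V.E), weekly (Section VII(c); Table 1 also labels its session columns as weeks). With none slipping, session 1 to session 12 spans 11 x 7 = 77 days.
- Last session to anhedonic retest: 0-10 days (Section V.F).

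**Inputs not given, so assumed**

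- g, days from first scan to session 1.
- s, days added by rescheduled sessions.

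**The plan's own figure.** The protocol does not derive the 12-13 weeks. The anhedonic time from initial assessment to retest is (0-7) + g + 77 + s + (0-10). With g = s = 0 this is 77-94 days, or 11.0-13.4 weeks. The control window of 84-91 days lies inside that range, so it is consistent with the nominal course.

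**Scan-to-scan interval, controls.** Counting from Day 1: 84 - 7 = 77 to 91 - 0 = 91 days, midpoint 84. If the initial assessment is read as the whole pre-treatment set including the Day 2 scan, and the clock starts there: 84-91 days, midpoint 87.5.

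**Scan-to-scan interval, anhedonic.** g + 77 + s + (0-10) days, midpoint 82 + g + s.

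| g | s | Anhedonic (days) | Midpoint | Minus control midpoint 84 | Minus control midpoint 87.5 |
|---|---|---|---|---|---|
| 0 | 0 | 77-87 | 82 | -2 | -5.5 |
| 3 | 0 | 80-90 | 85 | +1 | -2.5 |
| 7 | 0 | 84-94 | 89 | +5 | +1.5 |
| 7 | 7 | 91-101 | 96 | +12 | +8.5 |
| 7 | 14 | 98-108 | 103 | +19 | +15.5 |

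A positive difference means controls are retested sooner. With a Day 1 anchor the midpoint difference changes sign when g + s = 84 - 82 = 2 days. With a Day 2 anchor it changes sign at 87.5 - 82 = 5.5 days. In the first three rows the windows overlap under either reading. At g = 7, s = 7 they touch only at day 91. At g = 7, s = 14 they do not overlap.

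**Early stoppers.** Section VI says attempts will be made to keep assessing participants who leave treatment, but does not time their retest. If the final session means the last one attended, their interval can be shorter than the controls'.

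**The case against.** A reader might infer that controls are systematically retested sooner, by one to four weeks and always in that direction. The documents do not say so. With no wait and no slippage, controls are about 2 days longer at the midpoint. With a 7-day wait they are 5 days shorter, with overlapping windows. Larger gaps need late starts or slipped weeks that the protocol does not quantify, and early stoppers push the other way.

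The schedule is also not wholly open-ended. Table 1 ties sessions to weeks. The momentary-assessment (EMA) blocks begin the week after the first scan and run across the BA course, which suggests a start roughly a week after scanning. A missed session might be made up within the same week or not at all. All of this stands as a description of the intended course, but none of it is a limit.

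On consequences, the fMRI test includes Condition (gains against losses), so retest effects common to both conditions cancel. Bias there needs an effect that is both interval-dependent and condition-specific. The PRT contrast has no such protection. The baseline comparison and the pretreatment-predictor models do not use the control retest. These limits stand.

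Against this, a zero wait sits awkwardly with the plan. Baseline EMA is a pretreatment predictor, and Table 1 places an EMA assessment before session 1, yet EMA starts only the week after the scan. Because blocks are also described as running over the BA course, overlap with week 1 cannot be excluded. The zero-wait case is therefore unlikely but not ruled out.

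**Conclusion.** The concern holds in a limited form. The anchors differ, the control interval is bounded and the anhedonic interval is not, and the plan neither matches nor adjusts for the interval although it relies on controls to model retest effects.

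On nominal timing the mismatch is small: between 2 days longer and 5 days shorter for controls at the midpoint, for waits of 0 to 7 days and a Day 1 anchor. It grows by 7 days for each week of overrun. The windows separate fully in the example with an assumed 7-day wait and two slipped weeks. These figures rest on weekly sessions and on the assumed values of g and s; reading the control anchor as Day 2 moves every difference by 3.5 days in the controls' favour.

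The documents give no figure for how PRT practice or scan habituation varies with an interval difference of days or weeks, so neither the size nor the direction of any bias can be computed. This is an inexpensive improvement that protects the Group x Time and Group x Time x Condition contrasts. It does not show that those contrasts are biased.

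**What to change.** In Section V.F, time the control Post visit from the control's own Day 2 scan and PRT, and schedule it to match the anhedonic scan-to-scan interval. Early in recruitment, when there is nothing to match to, use the nominal interval and state its value. After that, use the running median among anhedonic participants already retested.

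Record the days between the two scan/PRT sessions for every participant, including those who stop BA early, and report the distribution by group. Where visits have already taken place, the interval can be derived from the visit dates.

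In Section VI (Statistics), add the interval as a covariate only in a sensitivity analysis of the Group x Time and Group x Time x Condition models. If the groups' intervals barely overlap, the covariate is confounded with group and the adjustment is extrapolation. Matching at the scheduling stage therefore matters more.

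The cost is a revised scheduling rule, one recorded variable and somewhat more scheduling work. Some controls would return later than they do now. No visit or procedure is added.
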